each investigator will enroll 2 lead-in subjects in-office undergoing tube placement using the TDS with local anesthesia facilitated by the Iontophoresis System (up to 100 subjects). Investigators may enroll into the pivotal cohort following completion of their lead-in procedures. The pivotal cohort will include 102 children ages 5 years and greater plus 120 children less than 5 years of age.

[figure not shown]
All pivotal and lead-in subjects will follow the same study protocol assessments and visit schedule consisting of a screening visit, procedure visit and a 3-week post-procedure follow-up visit. [REDACTED]

In addition, subjects will return for follow-up examinations every 6 months following the procedure until the tube implants have extruded, up to 24 months post-procedure. Otologic examination, tympanometry and audiometry will be conducted at the screening visit for all subjects (OR and in-office). Additionally, subjects treated in-office with local anesthesia (lidocaine iontophoresis) will undergo a cranial nerve physician exam at screening. The in-office lead-ins and pivotal cohort procedure will consist of local anesthesia of the tympanic membrane using the TULA Iontophoresis System with the lidocaine solution. Following iontophoresis, anesthesia of the TM will be assessed and tympanostomy tube placement will be conducted in anesthetized ears using the TULA Tube Delivery System. Subjects will return for a follow-up visit 3-weeks

ⁱ Subjects who are consented for the study will be considered enrolled. Throughout the protocol, enrollment numbers will reflect consented enrolled subjects with evaluable data. Enrolled subjects who are determined to be ineligible (screening failures), and enrolled subjects who withdraw prior to the study procedure are not included in the enrollment subject counts presented herein. Further definition of subjects included in the analysis sets is provided in Section 13- Statistical Methods

	post-procedure for otoscopic examination, tympanometry and audiometric assessment for all subjects with the addition of the cranial nerve exam for in-office subjects only. Follow-up assessments for tube duration at 6, 12, 18 and 24 months will consist of otoscopic examination and tympanometry. Lead-in procedures will be analyzed separately from the pivotal pediatric cohort.
Study Design:	Study Phase: Pivotal
	No. of Centers: Minimum of 15, maximum of 25 investigational centers
	Number of Arms: Single

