11.4.6. Audiometry

Audiometry will be employed to evaluate hearing status in each ear at screening (within 28 days prior to procedure) and at the 3-week post-procedure follow-up visit for all subjects age 4 years or older. Threshold testing will be conducted using air conduction and bone conduction at a minimum of 500, 1000, 2000 and 4000 Hz, and air conduction only at 8000Hz. Study sites will make efforts to measure hearing thresholds at all 5 frequencies. For younger subjects (less than 4 years of age), clinical study sites will attempt to collect audiometry at screening at a minimum of two frequencies for both air conduction (AC) and bone conduction (BC). The clinical study site audiologist will determine the most appropriate test method for each subject (visual reinforcement audiometry (VRA), conditioned play audiometry (CPA) or conventional audiometry). The method used at screening will be used for all follow-up assessments.

Audiometry is considered standard of care for this patient population and may be obtained prior to study informed consent as a screening assessment within 28 days prior to procedure.

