11.7.10. Unsuccessful Procedures

If the in-office procedure is not a success and the physician refers the subject for traditional OR TT placement, the Investigator will document the OR procedure TT placement success. Reasons for any OR procedural failures (of TT placement) will be documented. The OR procedure must take place within 2 months of the first in-office procedure. The subject must complete a post-procedure follow-up visit after the failed in-office procedure, at the protocol specified 3-week follow-up visit, or earlier if the OR procedure is planned prior to the 3-week visit. If no Tusker tube was placed, no additional follow-up visit is required following the subsequent procedure. If a Tusker tube was placed, the subject should follow the protocol-specified follow-up visit schedule to assess safety of the Tusker tube.

[REDACTED]

11.9.3-Week Post-Procedure Follow-Up Visit (+/- 7 Days)

[figure not shown]
1. All subjects are required to return for the 3-week post-procedure follow-up visit.
2. An otoscopic examination will be used to visually examine the condition of the external ear canal, TM, myringotomy, tube retention and patency.
3. The subject will complete the audiology and tympanometry, and cranial nerve physical exam (for in-office subjects only).
4. Subjects will be evaluated for any adverse events, and changes in concomitant medications will be recorded.

11.10. 6, 12, 18 and 24-month Post-Procedure Follow-Up Visits (+/- 28 days)

1. All subjects are required to return for additional follow-up visits through confirmation of tube extrusion (both ears if bilateral tube placement).
2. An otoscopic examination will be used to visually examine the condition of the external ear canal, TM, myringotomy, tube retention and patency.
3. The subject will complete tympanometry. If audiology is indicated, the study will collect audiometric data however there is no study requirement for audiology or audiology method for follow-up visits subsequent to the 3-week visit.
4. Subjects will be evaluated for any adverse events, and changes in concomitant medications will be recorded.
5. The subject will be exited from the study following confirmation of tube extrusion or completion of the 24 month visit if tube remains in place.

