14.3 Audiometric Assessments

Change in audiometric measurements (shifts) from baseline to the 3-week follow-up visit for subjects in the Safety Analysis Set will be presented using descriptive statistics (mean, SD, median, minimum and maximum). Shifts in air conduction (AC) and bone conduction (BC) hearing thresholds will be reported for each frequency (500, 1000, 2000 and 4000 Hz, and air conduction only at 8000Hz) and for each Cohort on a by-ear basis (treatment ears only). Shifts from baseline to each follow-up visit in air-bone gap (air conduction minus bone conduction) will also be reported for each frequency (500, 1000, 2000 and 4000 Hz) for each Cohort on a by-ear basis. Shifts in air conduction pure tone average (AC PTA), bone conduction PTA (BCA) and air-bone gap averages will be presented for each follow-up time point for each Cohort. For all PTA measurements, the PTA will be calculated by adding the threshold levels in decibels (dB) obtained at each frequency tested divided by number of frequencies tested.

Shift tables for air conduction pure tone averages greater than 15 dB (>15dB) by ear will be calculated, and presented for each Cohort for each follow-up time point.

Degree of hearing loss severity will be defined according to the protocol (slight through profound) and presented by subject for each Cohort and by relationship to study device, procedure or study drug.

Due to the differences in audiometric requirements for children dependent on age, all audiometry results will be presented by subjects less than 4 years of age, greater than 4 years of age, and overall.

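### SAP 14.3 averages PTA over whichever frequencies were tested at each visit, so a PTA shift, mainly under age 4, can reflect a change of frequencies rather than of hearing

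*SAP*

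**What the plan says.** SAP 14.3 plans shifts from baseline in air-conduction (AC) PTA, bone-conduction (BC) PTA and the air-bone gap average for each cohort and follow-up time point. It also plans a by-ear shift table for AC PTA changes above 15 dB. One definition serves every PTA: "the PTA will be calculated by adding the threshold levels in decibels (dB) obtained at each frequency tested divided by number of frequencies tested". The section shows no redaction at this point. It fixes no frequency set, no minimum number and no matching between visits. Shifts at each single frequency are reported as well, and all results are split at age 4 with an overall column.

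Protocol 11.4.6 governs what is tested:

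- From age 4: "Threshold testing will be conducted using air conduction and bone conduction at a minimum of 500, 1000, 2000 and 4000 Hz", plus 8000 Hz by AC only, with sites asked to make an effort to obtain all five.
- Under age 4: "clinical study sites will attempt to collect audiometry at screening at a minimum of two frequencies for both air conduction (AC) and bone conduction (BC". Which two is left open.
- Between visits: "The method used at screening will be used for all follow-up assessments". Method here means visual reinforcement, conditioned play or conventional audiometry.

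The protocol is not consistent on 3-week testing under age 4. Section 11.4.6 places audiometry at screening and "at the 3-week post-procedure follow-up visit for all subjects age 4 years or older", while the Protocol Summary (5.0) describes "tympanometry and audiometric assessment for all subjects with the addition of the cranial nerve exam for in-office subjects only". The 3-week visit section (11.9) and Table 4 (11.11) set no age limit. Exclusion 15 (10.10) lets children under 4 enrol without completing audiometry. For later visits, 11.10 says "there is no study requirement for audiology or audiology method for follow-up visits subsequent to the 3-week visit".

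Protocol 12.4 uses the same cut, AC PTA worsening of more than 15 dB, for investigator-diagnosed hearing loss. It does not name the frequencies either.

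**The concern.** An ear need not have the same threshold at every frequency. If the PTA at screening averages one set of frequencies and the PTA at follow-up averages another, their difference mixes any change in hearing with the difference between the two sets. The plan allows this: only the test method is held constant, and the youngest children may contribute any two or more frequencies.

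At stake is the audiometric safety summary. A mismatched pair can show a shift in an unchanged ear, push a modest true loss over the 15 dB cut, or hold a larger one under it. The study has a single arm, so no concurrent control would reveal such an artefact.

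**Working it through.** The documents give no figure to reproduce here, so the check applies the SAP's own formula.

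**Inputs.** The PTA rule is from SAP 14.3. The cut is a worsening above 15 dB (SAP 14.3, Protocol 12.4). The frequencies 500, 1000, 2000, 4000 and 8000 Hz (Protocol 11.4.6) are one octave apart and are numbered 0 to 4. The slope s of the audiogram is not in the documents; 5 and 10 dB per octave are assumed, and s = 0 is a flat ear.

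**Formula.** With a threshold of a + s × position, PTA = a + s × (mean position tested). For an unchanged ear:

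artefact = s × (mean position at follow-up − mean position at baseline)

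| Baseline → follow-up | Mean positions | Artefact | s = 5 | s = 10 | Slope needed for a false flag |
|---|---|---|---|---|---|
| 500+1000 → 500–4000 Hz | 0.5 → 1.5 | 1.0 s | 5 dB | 10 dB | above 15/1 = 15 |
| 500+1000 → 2000+4000 Hz | 0.5 → 2.5 | 2.0 s | 10 dB | 20 dB | above 15/2 = 7.5 |
| 500–4000 → 500–8000 Hz | 1.5 → 2.0 | 0.5 s | 2.5 dB | 5 dB | above 15/0.5 = 30 |

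If thresholds fall with frequency the sign reverses and the artefact looks like improvement. At s = 0 every entry is 0.

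**Audiograms that are not straight lines** (also assumed; dB at 500 to 8000 Hz): B = 35, 30, 20, 25, 30; C = 40, 35, 20, 25, 35; D = 45, 40, 15, 20, 30. With 2000+4000 Hz at screening, 500+1000 Hz at follow-up and no change in hearing:

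- B: 32.5 − 22.5 = 10 dB
- C: 37.5 − 22.5 = 15 dB
- D: 42.5 − 17.5 = 25 dB

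Only D exceeds the cut. Adding 8000 Hz to the other four moves these PTAs by 0.5, 1 and 0 dB.

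**Effect near the cut.** Observed shift = true change + artefact. In the first row of the table, a uniform true worsening is flagged above 15 − s if thresholds rise with frequency (10 dB at s = 5, 5 dB at s = 10). It is flagged only above 15 + s if they fall (20 dB and 25 dB). At s = 10:

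- True worsening of 10 dB, rising thresholds: reads 10 + 10 = 20 dB and is flagged. On common frequencies it reads 10 dB.
- True worsening of 20 dB, falling thresholds: reads 20 − 10 = 10 dB and is missed. On common frequencies it reads 20 dB.

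**Which combinations reach the cut.** Four frequencies give 11 sets of two or more, hence 121 ordered pairs. An apparent worsening above 15 dB arises in 0 pairs at s = 5 and 1 pair at s = 10. With 8000 Hz included there are 26 sets and 676 pairs, of which 0 and 27 exceed 15 dB. These counts give every combination equal weight and are not expected rates.

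**Overlap.** Of the 121 pairs, 6 share no frequency and 48 share exactly one, leaving 121 − 6 − 48 = 67 that share at least two. A matching rule therefore needs a stated minimum. Otherwise a single-frequency shift would be judged against a PTA cut.

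**The case against.** The affected group may be small. Protocol 11.4.6 words 3-week audiometry for age 4 or older and names only screening for younger children, and Exclusion 15 excuses them from baseline audiometry. From age 4 the protocol asks for the full set, so mismatch should be limited to incomplete audiograms. Tests after 3 weeks are done only if indicated. The artefact sizes rest on assumed audiograms. Safeguards exist: single-frequency shifts are reported, results are split by age, all eCRF data are listed per subject (SAP 21.0), and the Medical Monitor reviews adverse events (Protocol 12.5).

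Most of this stands, and it limits the weight of the point. It does not remove it. The single-frequency tables are unaffected, but they do not repair the PTA shifts or the 15 dB table. Splitting by age does not correct a mismatch within an ear. Carrying the method forward does not carry the frequencies.

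A reader might infer more than this, and the documents do not support it:

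- **That false hearing-loss flags will be frequent.** They need a steep audiogram and an unfavourable pair of frequency sets.
- **That the 120 of 222 pivotal children under 5 measure those exposed.** That group includes 4-year-olds and leaves out the lead-in cohorts, and the number tested at both visits is not given.
- **That the trial's conclusions are at risk.** The tables are descriptive.

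**Conclusion.** The point holds. Followed exactly, SAP 14.3 lets a PTA shift and the above-15 dB AC table reflect a change of frequencies, in either direction. The exposure lies mainly in children under 4 tested at both visits, hence in the under-4 and overall columns, and otherwise in any ear with an incomplete audiogram. How many such children there are cannot be determined while the protocol sections disagree.

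The size depends on the audiogram: nothing if it is flat, and 5 to 10 dB for two-then-four frequencies at the assumed 5 to 10 dB per octave. The practical risk is a true change moved across the 15 dB cut, more than a flag created from nothing. No hypothesis test or primary endpoint is involved. The correction should be made before analysis.

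**What to change.** In SAP 14.3:

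1. Compute each ear's shift in AC PTA, BC PTA and air-bone gap average only over frequencies measured at both visits being compared. For the gap, this means both AC and BC at both visits.
2. State in advance a minimum number of common frequencies, for example two, for entry to the PTA shift and above-15 dB tables.
3. Report by age group the number of ears below that minimum. Their data stay in the single-frequency shift tables.
4. Note any ear where the above-15 dB table differs from investigator-diagnosed hearing loss under Protocol 12.4, which does not fix the frequencies.

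Separately, reconcile Protocol 11.4.6 with 5.0, 11.9 and Table 4 on 3-week audiometry under age 4.

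The cost is SAP wording and a protocol clarification, using data already collected. Some ears leave the PTA shift table, and differences from the investigators' diagnoses need a note.

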	Enrollment: Up to 422, including 222 pediatric subjects in the pivotal cohort, and up to 100 lead-in OR and up to 100 lead-in in-office subjects.
Safety Measures	
Safety Evaluation will include the following assessments:
 
 • Otoscopic examination for visual inspection of external ear canal, TM condition at all visits (baseline, post-procedure and follow-up visits), with additional assessment of the myringotomy wound and tube at all protocol-specified follow-up visits. • Audiometry to assess hearing at baseline and at the 3-week post-procedure follow-up visit. • Tympanometry to assess tympanic membrane and middle ear conditions at baseline and at all protocol-specified follow-up visits. • Cranial nerve physical exam to assess cranial nerves CN VII (facial) and CN VIII (vestibulocochlear) at baseline, post-procedure and the 3-week post-procedure follow-up visit (in-office lead-in and pivotal subjects only). • Adverse events
Endpoints:	
Primary Endpoints:
 
 • Procedural Success: Proportion of subjects in the pivotal cohort with successful placement of Tusker Medical tympanostomy tubes in all indicated ears in an office procedure • Tube Placement Tolerability: Mean subject-reported pain score following TDS tube placement using the Faces Pain Scale-Revised (FPS-R) (pivotal cohort children ages 5 and older only)
	
Safety Endpoint:
 
 • Safety: Occurrence of adverse events, by subject
	
Secondary Efficacy Endpoints:
 
 • Tube Patency: Tube Patency is the proportion of subjects in the pivotal cohort, in which a Tusker Medical tube was successfully placed, with functionally patent tube(s) in all successfully treated ears at the 3-week post-procedure follow-up visit. • Tube Retention: Tube Retention is the proportion of subjects in the pivotal cohort, in which a Tusker Medical tube(s) was successfully placed, with presence of a Tusker Medical tube across the TM in all successfully treated ears at the 3-week post-procedure follow-up visit. • Anesthesia Effectiveness: Proportion of subjects in the pivotal cohort, who completed iontophoresis for all indicated ears, with adequate

anesthesia for TT placement in all treated ears as determined by physician's evaluation of TM anesthesia prior to tube placement.

Eligibility Criteria:	[REDACTED]

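### SAP 14.3 asks for hearing-shift tables at every follow-up, but after week 3 audiometry is done only when indicated, so the 6-24 month tables would describe a selected subset that cannot be compared with week 3

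*SAP*

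**What the plan says.** SAP 14.3 (Audiometric Assessments) uses two different time frames.

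- It opens with week 3 only: "Change in audiometric measurements (shifts) from baseline to the 3-week follow-up visit for subjects in the Safety Analysis Set" are to be described.
- It then widens. For air-bone gap: "Shifts from baseline to each follow-up visit in air-bone gap (air conduction minus bone conduction) will also be reported for each frequency". PTA shifts (air conduction, bone conduction and air-bone gap averages) are asked for at every follow-up time point. By-ear tables of air-conduction PTA shifts above 15 dB "will be calculated, and presented for each Cohort for each follow-up time point".
- PTA is the sum of the thresholds "obtained at each frequency tested divided by number of frequencies tested", so the set of frequencies is not fixed.

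The protocol schedules less.

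- The synopsis lists, under safety measures, "Audiometry to assess hearing at baseline and at the 3-week post-procedure follow-up visit". Section 11.4.6 and Table 4 agree, and the synopsis describes the 6-24 month visits as otoscopy and tympanometry.
- Section 11.10, on the 6-24 month visits: "If audiology is indicated, the study will collect audiometric data", but "there is no study requirement for audiology or audiology method for follow-up visits subsequent to the 3-week visit". The same section ends participation once tube extrusion is confirmed.
- Section 11.4.6 nevertheless states: "The method used at screening will be used for all follow-up assessments".

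**The concern.** The SAP asks for cohort summaries at four visits for which the protocol plans no cohort measurement. These tables would not be empty, because indicated audiograms are to be collected. They would be filled by whichever children had a reason for a hearing test and were still in the study.

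Protocol 12.4 uses a worsening of more than 15 dB in air-conduction PTA to diagnose post-treatment hearing loss. A table of shifts above 15 dB at 6, 12, 18 and 24 months would therefore be read as a series of hearing-loss rates, next to a 3-week figure from protocol-required testing. A difference between the two could reflect who was tested, by what method and at which frequencies, and not any change in hearing. Confirming safety is part of the primary objective in SAP 2.0, so the presentation matters even though it is descriptive.

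**Working it through.** **1. Visits side by side.**

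| Visit | Audiometry in the protocol | Shift outputs in SAP 14.3 |
|---|---|---|
| Screening | Required from age 4; attempted below age 4 | Baseline |
| 3 weeks | Required from age 4; same method as screening | Threshold shifts, air-bone gap shifts, PTA shifts, >15 dB table |
| 6, 12, 18, 24 months | Only if indicated; no method required; only children not yet exited | Air-bone gap shifts, PTA shifts, >15 dB table |

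The last row is the mismatch. No visible SAP text gives a denominator, a number-tested rule or a method restriction for those visits.

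**2. Is the wider time frame meant?** SAP 14.4 and 14.5 speak of each follow-up visit for tympanometry and otoscopy, which Table 4 schedules at all of them. SAP 14.6 names the 3-week visit for the cranial nerve exam, which stops there. On the SAP's own usage, a programmer would build 14.3 for all visits.

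**3. Sources of non-comparability after week 3.**

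- Who is tested: the indication rule in 11.10.
- Who is still present: exit on confirmed extrusion.
- How: 11.10 frees the method, while 11.4.6 appears to fix it.
- At what frequencies: PTA averages whatever was tested. Children under 4 may have as few as two baseline frequencies under 11.4.6, so baseline and later PTA can rest on different sets.

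**4. Size, as an illustration only.** The documents give no long-term hearing-loss or testing rate, so there is no plan figure to reproduce. Let r be the true share with a shift above 15 dB, a the chance of being tested if shifted, and b the chance if not shifted. Then

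rate among those tested = r·a / (r·a + (1 − r)·b).

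This exceeds r when a > b, equals r when a = b, and falls below r when a < b.

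Assume r = 2% and a = 80%, so r·a = 0.016. Scaling to the 222 pivotal children:

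| b | Number tested | Rate among tested |
|---|---|---|
| 10% | 222 × (0.016 + 0.098) ≈ 25 | 0.016 / 0.114 = 14.0% |
| 20% | 222 × (0.016 + 0.196) ≈ 47 | 0.016 / 0.212 = 7.5% |
| 50% | 222 × (0.016 + 0.490) ≈ 112 | 0.016 / 0.506 = 3.2% |

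Over r = 1-5%, a = 50-100% and b = 5-50%, the result runs from 1.0% (r = 1%, a = b = 50%, no bias) to 51.3% (r = 5%, a = 100%, b = 5%). That grid has no case with a < b, so by construction it cannot show understatement.

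Using all 222 as denominator does not help: the rate becomes r·a = 1.6% in the example, which is too low whenever some shifted children go untested.

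The sketch counts children, whereas the SAP table counts ears. It also ignores exits and missing baselines under age 4. It shows that the result depends on unknown testing patterns; it does not estimate the bias.

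**The case against.** **The wording may simply be loose.** The section opens with week 3 and only one follow-up audiogram is scheduled, so the plural could mean just that visit. This is possible, but the usage in SAP 14.4-14.6 points the other way, and the same edit settles either reading.

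**The direction of bias is not shown.** A reader might infer that the later tables would inflate hearing loss several-fold and make the cohort look as if it deteriorates. The documents do not support that. Protocol 11.10 does not define when audiology is indicated, and 11.4.6 calls audiometry standard of care, so some later tests may be routine. Documented hearing difficulty is among the indications in 11.4.1, and children retested for poor baseline hearing could improve. SAP 14.3 does not even say that the >15 dB table counts worsening only. This objection stands, and any multiple rests on assumed inputs.

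**Safeguards already exist.** Protocol 13.1 requires sample sizes and denominators, and SAP 21.0 lists all eCRF data by subject. A visible small n warns the reader but does not remove selection.

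**11.4.6 and 11.10 need not conflict.** The specific rule for late visits can be read as governing. That is reasonable, but 11.4.6 as worded covers all follow-up assessments, so a clause is still needed.

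**Redaction.** Visible SAP text jumps from 17.0 to 21.0, and other parts are blacked out. A rule could be there; nothing visible supplies one.

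**Conclusion.** The mismatch is clear on the visible text. SAP 14.3 as written produces 6-24 month air-bone gap shifts, PTA shifts and >15 dB counts from a selected subset of ears, possibly measured differently from baseline and not comparable with week 3.

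Overstated worsening is the probable result if suspected hearing problems prompt the tests. That is a condition, not a finding: direction and size cannot be determined from the documents, and the illustrative figures rest on assumed testing and hearing-loss rates.

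The outputs are descriptive. No primary or secondary test depends on them, and adverse events continue to be evaluated at the late visits. The change is worth making because the >15 dB threshold is the one the protocol uses to diagnose hearing loss and the correction is cheap.

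**What to change.** - **SAP 14.3:** limit the threshold, air-bone gap and PTA shift summaries and the >15 dB table to the 3-week visit.
- **Later audiograms:** present them in the subject listings, labelled as clinically indicated only, headed by the number tested out of the number attending each visit, with the method and, if captured, the reason for testing. Nothing visible shows that the reason is recorded, so the listing should not depend on it.
- **If any late summary is kept:** label it as a selected subset not comparable with week 3.
- **Protocol:** reconcile the same-method sentence in 11.4.6 with 11.10.

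The cost is SAP wording, one clarifying clause in the protocol, and the loss of formal late summary tables. Individual late audiograms captured on the eCRF stay visible in the listings, and late hearing-loss adverse events are still reported.
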